15.2 Recording and Reporting AEs, SAEs and SARs

AEs: All AEs that occur from day 1 of laser therapy up to and including the 12 week follow up visit (+/- 1 week) must be recorded on the eCRFs and in the patient medical notes.

The Principal Investigator is responsible for managing AEs at site according to the protocol. Seriousness and relation of the AE to the LLLT treatment should be assessed by the site PI. The Newcastle CTU will maintain a detailed central record of all AEs that occur. There is no requirement to inform sponsor of individual AEs.

SAEs and SARs: All SAEs that occur from day 1 of laser therapy up to and including the 14 month follow up visit (+/- 2 weeks) must be reported to the CI, Newcastle CTU and Sponsor immediately but no later than 24 hours of the site learning of its occurrence. Death should be reported as an SAE if it occurs within this period. If a death occurs after the 14 month visit it does not require reporting as an SAE but must still be recorded in the patient medical notes and eCRFs.

All SARs that occur from day 1 of laser therapy up to and including the end of study, as defined in section 13.10 must also be reported. SARs should be reported using the same process as for SAEs.

The initial SAE report will be made by the site PI completing the agreed SAE form which is sent via SOHO66 (secure fax to email system) to the Senior Trial Manager, Trial Manager, CI and nominated sponsor contact. The initial report can if necessary be made to the Clinical Trials Unit by telephone or e-mail and followed up formally using the SAE form. In the case of incomplete information at the time of initial reporting, or follow up information, a new SAE form must be completed and sent via secure system as soon as possible.

Contact details for reporting SAEs:

Trial Manager, Newcastle Clinical Trials Unit
[name], [contact] [name]

Please send the completed and signed SAE form(s) using the SOHO66 secure network

FAO LITEFORM TRIAL MANAGER to: TBC

All SAEs must be assessed for expectedness using the list of expected adverse events in LiTEFORM Protocol **section 15.2.1** and receive full review by the PI at site and discussed with the CI. It is encouraged that the CI consults with the Chair of the TSC and DMC.

For each SAE the following information will be collected:

• Full details in medical terms and case description

• Event duration (start and end dates, if applicable)

Action taken

Outcome

Seriousness criteria

Causality in the opinion of the PI

Whether the event is considered expected or unexpected.

Any change of condition or other follow-up information should be faxed to the Newcastle CTU as soon as it is available or at least within 24 hours of the information becoming available. Events will be followed up until the event has resolved or a final outcome has been reached.

Expected AE/ARs:

Most adverse events that occur in this trial, whether they are serious or not, will be related to the (C)RT that the patient is receiving as part of their standard care and not related to delivery of the LLLT.

The following are AEs that could be reasonably expected to occur in this population of patients who are undergoing (C)RT for HNC. It is expected that patients receiving primary or adjuvant radiotherapy \pm chemotherapy for head and neck cancers may require admission for symptom control of the following:

- Mucositis
- Dysphagia
- Pain
- Nausea and vomiting
- Weight loss
- Poor oral intake
- Infection
- Fatigue
- admission for hydration and/or feeding via NGT or Radiologically Inserted
 Gastrostomy (RIG) if the patient has one in situ

Patients may also experience tinnitus (chemotherapy related) and anaemia, although may not require admission for these symptoms.

15.2.1 Expected AEs after receiving LLLT:

- nausea
- dizziness
- increase in OM symptoms within 24 hours of receiving laser therapy
- decrease in OM symptoms within 24 hours of receiving laser therapy
- tingling sensation in the mouth
- feeling of warmth in the mouth

It the unlikely event that a patient experiences persistant or severe reactions to the laser therapy, the laser therapy must be discontinued immediately.

All occurrences of **expected** SAEs/AEs will be included in the first annual progress report but will not require completion of the SAE form or expedited reporting to REC. They must be recorded by the site on the eCRFs and in the patient notes. Treatment related AE and All SAEs will be reviewed by the DMC throughout the trial.

Coding:

AE's and SAEs must be coded using CTC version 4.0. SAEs will be recorded and reported according to category, severity (mild, mod, severe) and related-ness (definitely, probable, possible, unlikely, unrelated) to intervention.

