10. TRIAL DESIGN

This is a multi-centre (up to 10 regional cancer centres in England, Scotland and Wales), 2 arm parallel group, blinded randomised controlled trial (RCT). LiTEFORM aims to evaluate the effectiveness and efficiency of LLLT in reducing the severity and impact of OM in adult patients receiving (C)RT for HNC.

Patients will be randomised 1:1 to receive standard care plus LLLT (n=190) verses standard care plus sham LLLT (n=190). Both arms will receive the current standard care which includes optimisation of

good oral hygiene, hydration and use of analgesia, topical analgesics and coating gels for pain management. Treatment allocation will be stratified by two factors: 1. planned treatment (radiotherapy alone or chemo-radiotherapy 2. Unilateral or bilateral radiotherapy fields.

As part of the qualitative evaluation, a sample of patients who have consented or declined the main trial will be invited to take part in a telephone interview (n≤36). Staff at participating sites involved in trial recruitment/patient care, staff delivering LLLT, and other relevant members of the HNC team, will also be invited to take part in interviews. There will be observations of trial training and audio-recording of recruitment discussions (approximately 6-8 per site selected for analysis).

Pilot Study:

LiTEFORM includes a 9 month pilot phase (7 sites) with robust progression criteria to the full RCT (an additional up to 3 sites with a total of up to 10 sites). The pilot will look at all aspects of feasibility, safety and efficiency for LiTEFORM, with a qualitative process and economic evaluation. All 7 pilot sites will be set up as quickly as is possible during the pilot phase.

Progression Criteria:

Month 1 - Contractual start date and month funding starts from is 01 January 2017.

- Site set-up to be complete for 4 pilot centres by month 4 post funding, including the training of a minimum of 2 nurses or delegated staff to deliver LLLT in each centre to a competent level to ensure no gaps due to leave breaks etc. The second phase of an additional 3 centres to be set up by month 6.
- First 4 pilot centres recruiting on average 1.5 patients per month for the first 4 months post funding.
- First 4 sites recruiting at full rate, on average 2 patients per month from months 5 to 9 Post funding
- Additional 3 sites recruiting on average 1.5 per month during months 3 and 4.
- Additional 3 sites recruiting on average 2 patients per month during months 5-9.

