15. SAFETY REPORTING

15.1 Definitions

Term	Definition							
Adverse Event (AE)	AE) Any untoward medical occurrence in a participant, including occurrences which are not necessarily caused by or related to the intervention under trial.							
Adverse Reaction (AR)	An untoward or unintended response in a participant to which is related to the intervention under trial i.e. that a causal relationship between the trial intervention and an AE is at least a reasonable possibility and the relationship cannot be ruled out.							
	All cases judged by either the reporting medically qualified professional or the Sponsor as having a reasonable suspected causal relationship to the trial intervention qualify as adverse reactions.							
Serious Adverse Event (SAE)	 Results in death Is life-threatening* Requires inpatient hospitalisation or prolongation of existing hospitalisation Results in persistent or significant disability/incapacity Consists of a congenital anomaly or birth defect Other important medical events that jeopardise the participant or require intervention to prevent one of the above consequences * - life-threatening refers to an event in which the participant was at 							
	immediate risk of death at the time of the event; it does not refer to an event which hypothetically might have caused death if it were more severe.							
Serious Adverse Reaction (SAR)	An adverse event that is both serious and, in the opinion of the reporting Investigator, believed with reasonable probability to be due any dose of the trial intervention, based upon the information provided.							
Unexpected Serious Adverse Reaction (USAR)	A serious adverse reaction, the nature and severity of which is not consistent with the known information about the intervention under trial.							

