6. SAFETY

6.1 Adverse events

All adverse events (AEs) that occur from day 1 of laser therapy up to and including the 12 week follow up visit (+/- 1 week) must be recorded on the eCRFs and in the patient medical notes.

The severity of symptoms are graded using the Common Terminology Criteria for Adverse Events (CTC) 4.0. The CTC grades 1 through 5 with unique clinical descriptions of severity for each AE based on this general guideline:

- Grade 1: Mild; asymptomatic or mild symptoms; clinical or diagnostic observations only; intervention not indicated.
- Grade 2: Moderate; minimal, local or non-invasive intervention indicated; limiting age appropriate instrumental activities of daily living (ADL).
- Grade 3: Severe or medically significant but not immediately life-threatening; hospitalization or prolongation of hospitalization indicated; disabling; limiting self-care ADL.
- Grade 4: Life-threatening consequences; urgent intervention indicated.
- Grade 5: Death related to AE

Adverse events will be coded using the MedDRA dictionary and presented by preferred term, grouped by system organ class.

Treatment emergent adverse events, i.e. those that occur or worsen on or after first dose of study IMP, will be summarised by grade according to the worst grade experienced since day 1 of laser therapy. Data will also be presented separately for related (possibly, probably, definitely) and unrelated (unrelated, unlikely) events. The occurrence of non-serious adverse events will be tabulated, as required for EudraCT reporting. All data will be presented in the safety population by randomised treatment group.

Example Table 11: All adverse events by type: worst severity reported

	Laser (n =)	Sham (n =)
System Organ Class 1, n (%)		
Preferred Term		
Mild		
Moderate		
Severe		
Life-threatening consequences		
Death		
Total number affected		
Preferred Term		
Mild		
Moderate		
Severe		
Life-threatening consequences		
Death		
Total number affected		
System Organ Class 2, n (%)		
Preferred Term		
Mild		
Moderate		
Severe		
Life-threatening consequences		
Death		
Total number affected		

Example Table 12: Non-serious adverse events by type: worst severity reported (unrelated and unlikely causality)

	Laser (n =)	Sham (n =)
System Organ Class 1, n (%)		
Preferred Term		
Mild		
Moderate		
Severe		
Life-threatening consequences		
Death		
Total number affected		
Preferred Term		
Mild		
Moderate		
Severe		
Life-threatening consequences		
Death		
Total number affected		

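### Protocol 15.2.1 lists relief of mucositis symptoms as an expected adverse event, and SAP 6.1 has no rule to keep such records out of the harm tables

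*Protocol*

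**What the plan says.** Protocol 15.1 defines an adverse event as "Any untoward medical occurrence in a participant", whether or not it is related to the intervention. Protocol 15.2 requires recording of "All AEs that occur from day 1 of laser therapy up to and including the 12 week follow up visit", and gives the causality judgement to the site: "Seriousness and relation of the AE to the LLLT treatment should be assessed by the site PI".

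The list of expected events in 15.2.1 contains both "increase in OM symptoms within 24 hours of receiving laser therapy" and "decrease in OM symptoms within 24 hours of receiving laser therapy". Of expected events generally, the same section says "They must be recorded by the site on the eCRFs and in the patient notes". It also sends treatment-related AEs to the DMC throughout the trial.

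The purpose of the intervention is set out in Protocol section 10: "LiTEFORM aims to evaluate the effectiveness and efficiency of LLLT in reducing the severity and impact of OM". Protocol 9.3.2 makes adverse events attributed to LLLT part of the secondary safety outcome.

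SAP 6.1 tabulates all AEs by preferred term within system organ class, at worst grade (Table 11). It adds: "Data will also be presented separately for related (possibly, probably, definitely) and unrelated (unrelated, unlikely) events". Tables 12 to 14 split the non-serious events into unrelated, related and not assessable. Neither the text nor the table shells mention improvements.

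**The concern.** Listing both directions of symptom change means that the effect the trial hopes to see is also on its list of expected harms. The protocol gives sites two instructions that do not agree. Under the definition in 15.1, relief is not an adverse event and should not be recorded. Under the list and recording rule in 15.2.1, it is an expected event and must be recorded.

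Two things are at stake. Sites may have recorded differently, so the counts may partly reflect how each site read the protocol. And where relief was recorded, the related-event tables mix benefit with harm. If relief is recorded more often on laser, the safety comparison moves against the laser because it works. The grading adds to the difficulty, since the CTC grades in SAP 6.1 describe degrees of harm and an improvement has no natural grade.

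**Working it through.** The documents give no rate of recorded relief, so there is no stated figure to reproduce. The check is mainly one of text, with arithmetic to bound the effect.

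**1. Path from the list to the tables**

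| Step | Source | Result for a record of relief |
|---|---|---|
| Is it an AE? | Protocol 15.1 | No, if untoward is applied |
| Is it an AE? | Protocol 15.2.1 list | Yes, an expected one |
| Is it recorded? | Protocol 15.2.1 | Yes, if the site follows the list |
| Is it related? | Protocol 15.2 | Judged by the site PI, event by event |
| Is it tabulated? | SAP 6.1 | Yes in Table 11; if non-serious, also in Table 12, 13 or 14 according to causality |
| Is it removed anywhere? | SAP 6.1 | No rule found |

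The list defines the event by onset within 24 hours of a session, and 15.1 sets a low threshold for a causal link: a reasonable possibility that cannot be ruled out. A related judgement is therefore likely, but not automatic.

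**2. Weight of one patient**

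SAP 2.6 gives 87 randomised. Assume an even split and that all received at least one session, so that the safety population has 43 and 44 per arm.

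- 1/43 = 2.3 percentage points; 1/44 = 2.3 percentage points.
- This is a maximum within any one count. A patient already in that count for another related event adds nothing.
- The tables show the worst grade per patient, so repeated relief over the 3 × 6 = 18 scheduled sessions does not add further patients.

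**3. Direction and possible size, by illustration only**

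Let r be the true proportion with a related harm, equal in both arms. Let dS and dL be the proportions with relief recorded and judged related on sham and laser, independent of r. For a count of patients with any related event:

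- rate = 1 − (1 − r)(1 − d)
- false excess on laser = (1 − r)(dL − dS)

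With r = 20%, dS = 10% and dL = 30% (all assumed): sham 1 − 0.8 × 0.9 = 28%; laser 1 − 0.8 × 0.7 = 44%; excess 16 points, although true harm is equal.

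| Recorded relief, sham vs laser | r = 10% | r = 20% | r = 30% |
|---|---|---|---|
| 10% vs 20% | 9 points | 8 points | 7 points |
| 10% vs 30% | 18 points | 16 points | 14 points |
| 20% vs 50% | 27 points | 24 points | 21 points |

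If dL = dS the excess is zero, though both arms' rates are still raised. With the relief records removed it is zero in every row. Only the direction is general; the sizes follow from the assumed rates.

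**The case against.** Several points on the other side are sound.

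- **The list may serve only to classify expectedness.** Protocol 15.2 uses it to assess SAEs for expectedness. A site that applied the definition in 15.1 would not record relief. This stands, so it cannot be said that sites must have entered every improvement. The heading of 15.2.1 and its recording rule still support the other reading, and the SAP has no rule for the resulting differences.
- **Causality is judged case by case, under blinding.** The sham probe also produces warmth, so relief may be recorded and called related in either arm. This stands: any bias is the between-arm difference.
- **The SAP specifies no overall related-AE rate and no test between arms on AEs.** Relief coded to its own preferred term would be visible as a separate row. This stands, and it limits the damage. System-organ-class counts, and any total that a reader forms from Table 13, would still include it.
- **The DMC can see unblinded data** (Protocol 13.4), and nothing suggests that it saw only a pooled count. It could have recognised such records for what they were.
- **The protocol supplied is version 2.1, while the SAP cites version 4.0.** Whether the item survived is unknown.

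A reader might go further and infer that the laser's benefit is bound to be counted as related harm, or that a particular number of patients is affected. The documents support neither: recording and causality both depend on site judgement, and no rate of relief is given. A reader might also infer that the item duplicates the primary endpoint. It does not. It concerns change within 24 hours of a session, whereas the OMWQ-HN asks about the past week and the primary outcome is the week 6 score.

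**Conclusion.** The conflict between Protocol 15.1 and 15.2.1 is plain in the text, and SAP 6.1 does not resolve it. Records of symptom relief can therefore reach Tables 11 and 13 as adverse events, and could have reached the DMC's review of related events. If they are more frequent on laser, related events on laser are overstated.

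How much is unknown. The bound of about 2.3 points per affected patient assumes an even split of the 87 and that everyone had at least one session. The excesses in the illustration rest wholly on assumed rates and on independence, and they apply to an any-related-event count that the SAP does not itself specify. There may be no such records at all. The week 6 OMWQ-HN analysis is untouched. This is a gap in how harms are tabulated, worth closing because the rule is specific and cheap.

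**What to change.** The last visit was on 27 October 2019 (SAP 2.6), so a change to the protocol or a note to sites can no longer alter what was recorded. The change that matters is in SAP 6.1.

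**SAP 6.1.** Add a rule along these lines: before unblinding, a reviewer without access to allocation will examine the AE terms and identify records that describe an improvement in OM symptoms; these will be excluded from Tables 11 to 14 and their number reported by arm on a separate line. Records of worsening stay in the tables. A term whose direction cannot be determined should also stay in. Fixing the rule before unblinding matters because the exclusion could favour one arm.

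**Protocol.** If the item is still in the current version, reconcile 15.1 and 15.2.1 by removing it from the expected-event list.

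The cost is a sentence or two in the SAP, one bullet in the protocol if it is still there, and a short blinded review of AE terms.

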15.3 Recording and Reporting USARs

All USARs occurring from day 1 of laser therapy up until the end of study must be reported to the NHS REC. The sponsor will perform this reporting.

The assessment of expectedness will be performed by the CI against the known information for the trial as per the trial protocol.

USARs must be reported no later than 15 calendar days after the sponsor has first knowledge of the event. Any relevant follow-up information should be sought and reported as soon as possible after the initial report.

As soon as a site suspects that a SAR may be a USAR they must contact the CI, sponsor representative sponsor is in receipt of a minimum set of information:

- Sponsor trial reference and trial name (sponsor reference)
- Patient trial number and date of birth

- Name of intervention
- Date of notification of the event
- Medical description of the event
- Date and time of the onset of the event (including event end date if applicable)
- Causality assessment
- Seriousness of the event, particularly if life threatening or fatal
- An identifiable reporter (e.g., Principal Investigator)

This information must be provided by email. The site is expected to fully cooperate with the sponsor in order that a full and detailed report can be submitted to the NHS REC within the required timelines.

PIs will be informed of all USARs by the sponsor.

15.4 Responsibilities

Principal Investigator

- Checking for AEs and ARs when participants attend for laser therapy or at the week 12 follow-up
- Using medical judgement in assigning seriousness and causality and providing an opinion on expectedness of events.
- Ensuring that all SAEs and SARs, including USARs, are recorded and reported to the sponsor within 24 hours of becoming aware of the event and provide further follow-up information as soon as available.
- Ensuring that AEs and ARs are recorded and reported to the sponsor in line with the requirements of the protocol.

Chief Investigator

- Clinical oversight of the safety of trial participants, including an ongoing review of the risk/benefit.
- Using medical judgement in assigning seriousness, causality and expectedness
 of SAEs where it has not been possible to obtain local medical assessment.
- Using medical judgement in assigning expectedness to SARs.
- Immediate review of all USARs.
- Review of specific SAEs and SARs in accordance with the trial risk assessment and protocol.

Sponsor

- Assessment of expectedness of any USARs
- Expedited reporting of USARs to the REC within required timelines
- Notification of all investigator sites of any USAR that occurs

TSC/DMC

 Reported to DMC/ TSC Review of safety data collected to date to identify any trends

15.5 Notification of Deaths

All deaths from day 1 of laser therapy up to and including week 12 follow up will be reported as SAEs irrespective of the cause of death and reported to the sponsor, CTU and CI. All deaths will be reported to the DMC.

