4. TRIAL SUMMARY

Trial Title A Randomised Controlled Trial of the Clinical and Cost

Effectiveness of Low Level Laser in the Management of Oral

Mucositis in Head and Neck Cancer Irradiation

Acronym LiTEFORM

Summary of Trial Design A multicentre blinded randomised controlled trial of low level laser

versus sham low level laser therapy (LLLT) in the prevention and management of oral mucositis in head and neck cancer irradiation

Summary of Participant

Population

Adults (≥18 years) referred for head and neck cancer irradiation

Planned Sample Size 380 adults (190 per arm)

Planned Number of

Sites

Up to 10 sites (including 7 pilot sites)

Intervention Duration 6 weeks after first LLLT

Follow Up Duration 14 months after last LLLT

Planned Trial Period 47 months

Intervention Low Level Laser Therapy (LLLT)

Primary Outcome: OMWQ-HN score at week 6 following start of LLLT treatment.

Primary Objective: To compare the clinical effectiveness and cost effectiveness of LLLT plus

standard care vs standard care alone as measured by the Oral Mucositis Weekly Questionnaire-Head and Neck Cancer (OMWQ-HN) in adult

HNC patients receiving (C)RT.

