8.1 Risk Assessment

The laser is being used within the CE (Conformité Européenne) marked indication for reducing pain and inflammation for patients with OM.

Class 3b lasers are potentially harmful to the retina. This hazard can be reduced with the provision of laser glasses from the device manufacturer which must be worn by both the practitioner and the patient whilst the device is in operation. The eye protection can be worn over prescription glasses. The risk of unintended laser irradiation of the eye will also be reduced through the removal and covering of reflective surfaces in the treatment area. The door of the treatment area will be locked and a sign displayed to indicate the use of laser therapy.

Before the treatment starts the operator will ask the patient to report if the light from the laser becomes too hot. If the heat becomes excessive, the laser will be stopped and the probe allowed to cool down.

The laser must not be used over the pregnant uterus, but will only be used in the oral cavity for this trial. Although in line with manufacturer recommendations the laser can be used with caution in pregnant women, women who are known to be pregnant at the time of their treatment, or are planning to become pregnant, will not be eligible to take part in LiTEFORM. Each participating site will follow their standard protocols for (C)RT, which ensure that women of childbearing age are not pregnant whilst undergoing their (C)RT. If a woman is reported to become pregnant during the treatment, LLLT treatment will be stopped immediately. The patient will be followed for the duration of the trial for outcomes unless she withdraws from the trial.

There is some anxiety amongst physicians that if the laser can stimulate healing of normal cells, that it may have a preserving effect on cancer cells. At present the effects of LLLT on tumour behaviour have been inadequately studied. There are a few published in vitro studies. These studies have inconsistent results, which may reflect varying dosimetry and power of the laser. Although there are no case reports of adverse outcomes following LLLT, it remains biologically plausible that LLLT may have an adverse impact on tumour behaviour resulting in poorer outcome and survival. This trial will

aim to address this question by collecting and reporting tumour recurrence and progression during the study period.

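### Protocol sections 15.2 and 15.5 give different end points for reporting deaths as SAEs: the 14 month visit and the week 12 follow-up

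*Protocol*

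**What the plan says.** Protocol section 15.2 sets two windows, both starting on day 1 of laser therapy. The one for adverse events closes at the week 12 visit (give or take one week). The one for SAEs closes at the 14 month visit (give or take two weeks), with a report to the chief investigator, the trials unit and the sponsor within 24 hours of the site learning of the event. On deaths in the SAE window it says: "Death should be reported as an SAE if it occurs within this period". A death after the 14 month visit needs only an entry in the notes and the eCRF.

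Protocol section 15.5, which deals with deaths alone, says: "All deaths from day 1 of laser therapy up to and including week 12 follow up will be reported as SAEs", whatever the cause, and names the same three recipients. It then adds, with no time limit: "All deaths will be reported to the DMC".

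Protocol section 8.1 explains why late deaths matter in this trial: "it remains biologically plausible that LLLT may have an adverse impact on tumour behaviour resulting in poorer outcome and survival". Section 9.2 makes long-term survival risk a secondary objective.

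**The concern.** Both sections are current text and both tell a site when a death is to be sent as an SAE, yet they stop about a year apart. Week 12 is where section 15.2 ends adverse event recording, not SAE reporting, so 15.5 appears to carry the wrong one of the two limits.

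An investigator who turns to the section on deaths and stops there could reasonably conclude that a death at, say, month 8 needs no SAE report. That death would then miss the 24-hour notification. It would also miss the investigator's opinion on cause and the judgement of expectedness that go with an SAE report. Those assessments decide whether an event is treated as a serious adverse reaction or an unexpected one, and sections 15.2 and 15.3 keep those two duties running to the end of the study. The SAP's line listing of SAEs (section 6.2) has columns for causality and expectedness, so a death not sent as an SAE could be absent from it. If sites chose differently between the two sections, reporting would also vary by site.

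**Working it through.** The plan gives no figure on this point, so there is none to reproduce. The check has two parts.

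**The two rules side by side**

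| | Section 15.2 | Section 15.5 |
|---|---|---|
| Start | Day 1 of laser | Day 1 of laser |
| End | 14 month visit | Week 12 follow-up |
| Cause of death | Any | Any |
| Deadline | 24 hours | None stated |
| Recipients | Chief investigator, trials unit, sponsor | The same three; all deaths also to the DMC |
| Deaths after the end point | Notes and eCRF only | Nothing said, beyond the DMC sentence |

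The two agree on start, scope and recipients. They differ on the end point.

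**How much follow-up lies between the two end points**

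Inputs:
- Treatment lasts 6 weeks (Protocol section 4: "Intervention Duration 6 weeks after first LLLT").
- Month 14 is counted from the last laser session (Protocol section 4: "Follow Up Duration 14 months after last LLLT"; SAP section 4.1.2.2 agrees).
- Week 12 is counted from the first laser session (SAP Table 1).
- One month is 30.44 days, or 4.348 weeks.

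Formula: share = (end of 15.2 window − end of 15.5 window) ÷ (end of 15.2 window), all measured from the first laser session.

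Main reading: the 15.2 window ends at 42 + 14 × 30.44 = 468 days (66.9 weeks). The 15.5 window ends at 12 × 7 = 84 days. Share = (468 − 84) ÷ 468 = 384 ÷ 468 = 82%.

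Other readings, in weeks:

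| Reading | Calculation | Share |
|---|---|---|
| Month 14 counted from first session | (60.9 − 12) ÷ 60.9 | 80% |
| Main reading, week 12 visit a week late and month 14 visit two weeks early | (64.9 − 13) ÷ 64.9 | 80% |
| Main reading, week 12 visit a week early and month 14 visit two weeks late | (68.9 − 11) ÷ 68.9 | 84% |
| Week 12 counted from last session (contrary to SAP Table 1), month 14 from last | (66.9 − 18) ÷ 66.9 | 73% |
| Week 12 counted from last session, month 14 from first | (60.9 − 18) ÷ 60.9 | 70% |
| Followed only to 4 months after last session | (23.4 − 12) ÷ 23.4 | 49% |

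The last row is for participants who did not start laser before 6 July 2018. After early closure, SAP sections 2.6 and 3.1 end their follow-up at the 4 month visit. The row assumes that their SAE window closes at that visit.

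**The case against.** The strongest reply is that the two sections can both be obeyed. Section 15.5 does not say that only deaths to week 12 are SAEs, and it does not release a site from reporting later ones. Section 15.2 covers later deaths in express words and holds the SAE form process and the 24-hour deadline. Section 15.4 repeats the investigator's duty to report all SAEs with no week 12 limit. A site that follows 15.2 breaches nothing. This stands, and it limits the point to two stated windows that differ. It does not remove the point: if 15.2 governs, the week 12 limit in 15.5 does no work, and an upper limit in the section on deaths invites the shorter reading.

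A reader might go further and infer that deaths after week 12 are lost to the survival analysis. The documents do not support that. Protocol section 13.6 records death at month 14, and section 16 defines survival by date of death, so the survival data do not rest on the SAE form. One qualification is that participants followed only to 4 months have no month 14 record. The schedule in section 13.7 also marks clinical outcomes during treatment and at month 14, but not at month 4.

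A reader might also infer that the DMC would learn of late deaths late. Section 15.5 sends all deaths to the DMC without limit of time. It gives no deadline for doing so, and section 20 has the DMC receiving aggregated data at least annually, so delay is possible but is not shown.

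**Conclusion.** The inconsistency is real and should be corrected. It is a contradiction between two reporting windows and invalidates no planned analysis. Between 80% and 82% of planned follow-up lies between the two end points, depending on where month 14 is counted from, and about half for participants followed only to 4 months. What is at risk, at a site that follows 15.5, is the 24-hour report to the sponsor, trials unit and chief investigator, and the causality and expectedness assessment, for deaths after week 12.

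The shares are of calendar time, not of deaths. A reader might take 82% to mean that most deaths fall in the disputed period, but the documents give no death rate or timing from which to say so. Nor do they show that any site followed the shorter window.

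The protocol supplied is version 2.1, while the SAP refers to version 4.0. Whether 15.5 was later corrected cannot be checked from these documents.

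**What to change.** Reconcile the two sections by giving 15.5 the end point already explicit in 15.2, so that deaths from day 1 of laser to the 14 month visit inclusive are reported as SAEs, and leave the DMC sentence as it is. First confirm whether version 4.0 already does this.

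The SAP records that the last patient visit has taken place, so the more useful step now is a check of the data. Compare every death after week 12 in the eCRF with the SAE records, and obtain any missing report with date, cause, causality and expectedness before the SAE line listing is produced.

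The cost is one phrase in the protocol, one reconciliation of deaths against SAE records, and a few extra SAE forms.
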